3.4 Administration

The steps with yoga mat include:

For yoga:

1.Crescent lunge pose:

- Participants will be instructed to start in the Facing Downward as Dog Pose.
- All participants will be instructed to inhale and simultaneously raise the right leg behind them and exhale as they step the right foot forward between their hands.
- All of them will be asked to make sure that the right knee is aligned above the right ankle.

2. Warrior II pose:

- Participants will be instructed to start in mountain pose (Tadasana).
- All of them will be instructed to step their left foot back, extend their arms out, position their hips, and bend deeply into the right knee while gazing directly above their right middle finger.
- At that position, all will be instructed to breathe, hold, and strengthen.
- Then, all will be asked to step back into mountain pose.

3.Triangle pose:

• Participants will be instructed to stand straight with their legs apart. The distance between their legs will be a little more than the span of their shoulders.

- All will be instructed to inhale, to raise their right hand straight above their head, and will be asked to maintain the right arm parallel to the right ear.
- All of them will be instructed to exhale, to bend their torso at the waist, to their left side.
- Simultaneously, all will be asked to slide their left arm down along their left leg until their fingers reach their ankle.
- At that point, their right arm will be instructed to be horizontal as their head tilts left.
- All will be asked to hold the pose with their knees and elbows straight and to inhale. Everyone will be instructed to straighten themselves and stand erect. All will be asked to repeat the posture on the other side.

For Deep Breathing:

The participants will be seated on chairs and will be given a 3-minute, 6 deep breaths per minute session along with the CP protocol 5 times a week for 3 weeks.

Conventional physiotherapy:

In the first two exercises, which will include a heel raise and a toe raise, the focus will be on the strength and power of the plantar flexors and dorsiflexors. The exercise will be modified by 1) performing it on the ground or over the edge of a 10-cm step, 2) using both legs or one leg, and 3) adjusting the amount of upper extremity support to determine the progression of the exercise. The starting difficulty for the heel and toe raises will be adjusted to allow the participant to complete two sets of ten to fifteen repetitions.

A single-leg stand will be the third exercise, focusing on lower extremity stability and postural control. The identical hand position progression that will be used for the heel and toe rises

should be employed by the participants. The single-leg stand will be performed by the participants for two repetitions on each leg for 30 seconds to 1 minute.

A gastrocnemius stretch will be the final exercise. To feel a comfortable stretch in their gastrocnemius, participants will simultaneously lower their heel and lean forward while placing the ball of their foot onto the edge of the 10-cm step. Each leg should be stretched separately for 30 seconds to 1 minute, and the participants will be asked to execute the exercise twice during each training session.

3.5 Assessment & Outcomes Measures

3.5.1 Primary outcomes

Tampa scale:

The Tampa scale will initially be used to distinguish between non-excessive fear and phobia in patients with chronic musculoskeletal pain, i.e., the fear of movement. In its original form, the TSK will be a 17-item assessment checklist. It will use a 4-point Likert scale (Strongly Disagree-Disagree-Agree-Strongly Agree) with statements that will later be linked to the model of fear-avoidance, fear of work-related activities, fear of movement, and fear of re-injury.

Cumberland ankle instability tool (CAIT):

The Cumberland Ankle Instability Tool (CAIT) will be a 9-item, 30-point scale that will measure the severity of functional ankle instability. Using a numeric value, the

Cumberland Ankle Instability Tool (CAIT) will have the ability to discriminate between stable and unstable ankles.

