2.1 Background & Aims

Yoga is an Indian mind-body practice that has become well-known all over the world. During standing, sitting, and lying supine or prone, participants' bodily motions are gradual and have a wide range of motion. It has been demonstrated that yoga practice improves balance, coordination, emotional and mental well-being which assist in increasing joint flexibility, range of motion (ROM) and muscle strength.

Three yoga poses namely; the crescent lunge pose (Halasana), warrior II pose (Virabhadrasana II), and triangle pose (Trikonasana). These yoga manoeuvres reduce pain, which enhances people's quality of life. Reports indicate that yoga alters the perception of pain and influences brain waves. Since yoga promotes both pain treatment and psychosocial healing, it has been a popular alternative pain management technique in recent years for Kinesio phobia.

Injured athletes can benefit from deep breathing as a non-pharmacological pain management technique that increases localized tissue circulation and diverts attention from their discomfort. Inducing a shift in sympathetic nervous system activity by reducing stress hormone levels and activating the diaphragm by stimulating the vagal nerve, which regulates pain perception, guided or focused deep breathing functions as a mindful meditation technique.

The most successful strategy for collegiate athletes to handle stress and prepare for competition was deep breathing. Additionally, it has been demonstrated that deep breathing can assist individuals with chronic musculoskeletal pain manage their condition effectively, reducing movement fear and enhancing subjective wellbeing and quality of life.

Conventional physical therapy includes exercises for strengthening and flexibility as well as training for agility and balance. These therapies aim to improve muscular strength, speed, agility, and neuromuscular control; restore a normal gait pattern without the use of assistive devices; improve balance; and increase range of motion and flexibility. Conventional physiotherapy uses a range of techniques centered on function restoration, strength enhancement, and injury prevention to address these problems.

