3.1 Research Design Outline

The study aims to perform a comparative study on chronic ankle instability with Kinesio phobia in Saveetha college of physiotherapy and Saveetha college of allied health sciences.

Formerly titled "Effectiveness of Three Typical Yoga poses and Conventional Physiotherapy for Kinesio phobia Among Football Players with Chronic Ankle Instability: A Comparative Study" involves amateur football players with Kinesio phobia by using the Tampa scale for Kinesio phobia and Cumberland ankle instability tool for Chronic ankle instability. The outcome is the total fear of movement, and fear of re-injury, severity of functional ankle instability. Total scores of 68 for Kinesio phobia, 30 for chronic ankle instability. Higher score means a better outcome.

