4.1 Primary Outcomes

The primary analyses will compare experimental vs control group guidelines on their mean and standard deviation: (i)Tampa scale, (ii) Cumberland ankle instability tool (CAIT).

Comparison will be tested by using the Paired t test to find the significant difference within the intervention effects and between the two groups (Experimental control group and Experimental Group) using independent t-test. P values <0.05 has been considered statistically significant.

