4.2 Secondary Outcomes

The primary analyses will compare experimental vs control group guidelines on their mean and standard deviation: (i) Y-balance test (ii) Pain anxiety symptom scale.

Comparison will be tested by using the Paired t test to find the significant difference within the intervention effects and between the two groups (Experimental control group and Experimental Group) using independent t-test. P values <0.05 has been considered statistically significant.

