4.3 Missing Data

For players who do not attend the assessment, the mean imputation of the assessment scores from their allocation group has been used.

5. Informed Consent Forms (ICF)

Written consent will be gained from the amateur football players with Kinesio phobia along with chronic ankle instability using the consent forms attached to the application.

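### No outcome counts ankle re-injury, and players absent through injury receive their own group's mean, so injury-related absence that differs between groups would exaggerate benefit in the worse-hit group

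*Combined protocol and SAP*

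**What the plan says.** All four outcomes are scores. Section 3.1 sets the scope: "The outcome is the total fear of movement, and fear of re-injury, severity of functional ankle instability". Section 3.5.1 names two primary outcomes. The first is the Tampa scale, built from "statements that will later be linked to the model of fear-avoidance, fear of work-related activities, fear of movement, and fear of re-injury". The second is the CAIT, a 9-item, "30-point scale that will measure the severity of functional ankle instability". Sections 3.5.2 and 4.2 add the Y-balance test and the Pain anxiety symptom scale (PASS). None of these sections counts sprains, giving-way episodes or withdrawals for injury.

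The groups are compared by the test in section 4.1: "between the two groups (Experimental control group and Experimental Group) using independent t-test".

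Section 4.3 has one rule for absence: "For players who do not attend the assessment, the mean imputation of the assessment scores from their allocation group has been used". It does not distinguish reasons for absence, and no sensitivity analysis is planned.

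Two other places give context. Section 2.1 describes conventional physiotherapy as using "techniques centered on function restoration, strength enhancement, and injury prevention". Section 3.4 varies the heel and toe raises by surface, by one or both legs, and by "adjusting the amount of upper extremity support to determine the progression of the exercise".

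**The concern.** These players have unstable ankles and fear hurting them again. The plan measures the fear but not the event, although its own rationale mentions injury prevention. Read alone, a fall in fear of movement does not tell a reader whether re-injury stayed level or rose.

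The missing-data rule adds to this. Absence from the assessment is the natural consequence of a fresh ankle injury, and players absent for that reason would be expected to score worse than attenders. Section 4.3 treats them as typical attenders. If one group loses more players this way, its results on every outcome are flattered, and the planned tables would contain nothing to show it.

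This is a different matter from the understated variance that mean imputation also causes. Correcting the variance would leave both the shift in the mean and the missing injury count in place.

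**Working it through.** **Inputs.** From the documents: CAIT out of 30 (section 3.5.1), own-group mean imputation (section 4.3), independent t-test at 0.05 (section 4.1). The text gives no sample size, SD, dropout rate or injury rate, so there is no planned figure to reproduce, and every rate below is an assumption.

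**Step 1: what the rule does to a group mean.** Let a group have n players, of whom m attend with mean A. Filling the other n − m with A gives (m × A + (n − m) × A) / n = A. Absent players have no influence on the mean.

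**Step 2: bias in one group.** Suppose a fraction f is absent through injury and truly scores d points worse than attenders, with any other absentees like attenders. The true mean is (1 − f) × A + f × (A − d) = A − f × d. The reported mean is too favourable by f × d.

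**Step 3: bias in the comparison.** Bias = f_E × d_E − f_C × d_C (E experimental, C control).

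- Only one arm affected, low end: 0.05 × 4 = 0.2 CAIT points.
- Only one arm affected, high end: 0.15 × 10 = 1.5 CAIT points, which is 1.5 / 30 = 5% of the scale.
- Both arms affected unequally (15% and 5%, d = 10): 1.5 − 0.5 = 1.0 point.
- Both arms affected equally: 0.

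**Step 4: exaggeration or reversal?** Work in SD units. Assume that attenders in the experimental arm do 0.5 SD better than control, that injured absentees do 2 SD worse than control (so d = 2.5 SD), and that only the experimental arm is affected. The true difference is 0.5 − f × 2.5, which reaches zero at f = 0.5 / 2.5 = 20%. The rule reports +0.50 SD throughout. At f = 15% the true difference is 0.5 − 0.375 = +0.125 SD.

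A simulation with 30 players per arm (20,000 runs, two-sided test at 0.05) gave these rates of a significant result favouring the experimental arm:

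| Injured and absent | True difference | Real scores of all players | Attenders only | Section 4.3 rule |
|---|---|---|---|---|
| 10% | +0.25 SD | 10% | 46% | 50% |
| 20% | 0.00 SD | 0.7% | 43–44% | 51–52% |
| 30% | −0.25 SD | 0.1% | 42% | 55% |

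Most of the distortion is already present with attenders only, so it comes from leaving injured players out. The remainder comes from the understated standard error. It follows that dropping the imputation alone would not remove the bias.

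**The case against.** Several points on the other side stand.

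- **Reversal is not shown at modest rates.** A reader might infer that a harmful programme could be reported as a success. Under the assumptions above, that needs more than 20% of one arm to be both injured and absent, with little or no such loss in the other. At 5–15% the true difference stays positive and is overstated. Nothing in the documents points to the higher rates.
- **The loading may be shared.** The step raises and single-leg stands are listed under conventional physiotherapy. Section 2.1 describes combining that with yoga and breathing, and section 3.4 gives the breathing alongside it. Arm composition is not clearly stated, so these exercises are no evidence that injury would differ between arms. They are also graded: the raises may be done on the ground or on both legs, with the starting difficulty set to what the player can complete. The documents do not show them to be unsafe.
- **Masking is partial.** An injured player who attends is scored normally, and CAIT can register a worse ankle.
- **Planned is not the same as recorded.** A reader might infer that no injury would be noted anywhere. Part of section 5 before 5.2 is not in the public text, so the most that can be said is that the outcome and analysis sections plan no such count.
- **Mode of completion.** Only PASS is described as self-report. That Tampa and CAIT can be completed away from the site is a reasonable expectation, not something the plan states.

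None of this alters the mechanism. The rule in section 4.3 ignores the reason for absence, and the planned data would not let a reader see whether injury-related absence was balanced.

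**Conclusion.** The point holds in a limited form. The visible plan counts no re-injury, and section 4.3 removes any influence that a player absent through injury would have on the group mean. The comparison is biased to the extent that f × d differs between arms: 0.2 to 1.5 CAIT points if one arm is affected at the assumed 5–15% and 4–10 points, and nothing if the arms are equally affected. The expected consequence is exaggerated benefit. Concealed net harm would need much higher one-sided rates than those assumed here, and the documents give no grounds for expecting them. How likely any of this is cannot be judged, because neither a sample size nor an injury or dropout rate is stated. The CAIT range does not carry over to Tampa, for which no figure was computed. The change is worth making because it is cheap and because reasons for absence are hard to reconstruct afterwards.

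**What to change.** 1. **Section 4.3, data collection.** Record the reason for each non-attendance. Seek Tampa, CAIT and PASS by phone or form from players who cannot attend, after confirming that the versions used can be completed that way. The Y-balance test would then be the main score still missing for an injured player.
2. **Section 4.3, analysis.** Replace own-group mean imputation with an analysis of observed scores, or with multiple imputation using baseline scores. Either still treats absentees as resembling attenders in some respect, so add a sensitivity analysis that gives players absent through injury unfavourable scores on all outcomes, including Y-balance. Before doing so, reconcile the direction of the Tampa scale: section 3.1 says that higher is better, while section 3.5.1 describes a measure of fear.
3. **Sections 3.5.2 and 4.2, injury count.** Record ankle sprain, giving-way, or stopping because of injury, using one fixed question at existing sessions and at the final assessment. Report the number of players with at least one event by group, beside the primary results. No rule making the Tampa conclusion depend on these counts is proposed, since there is no criterion for it.

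**Cost.** One line on the session sheet, an absence-reason field, a few phone calls, one extra table and one additional analysis. No new staff or procedure is needed. The small downside is that questionnaires completed remotely differ in mode from those completed on site.

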3.5.2 Secondary outcomes

Y-balance test:

Absolute reach distance (cm) = (Reach 1 + Reach 2 + Reach 3) / 3. Relative (normalised) reach distance (%) = Absolute reach distance / limb length * 100 Composite reach distance (%) = Sum of the 3 reach directions / 3 times the limb length * 100.

Pain anxiety symptom scale:

Pain and anxiety symptom scale (PASS) is a 20-item self-report measure to assess painrelated anxiety. Each item is a 6-point scale anchored from 0 (never) to 5 (always). Total score is ranged from 0 (representing no pain anxiety) to 100 (representing severe pain anxiety.

4. Statistical Analysis Plan (SAP)

Descriptive and inferential statistics will be used. Normally distributed data will be presented by mean and standard deviation (SD), and non-normally distributed data will be presented by median and interquartile range. SPSS (version 24.0) will be used for all statistical analyses.

4.1 Primary Outcomes

The primary analyses will compare experimental vs control group guidelines on their mean and standard deviation: (i)Tampa scale, (ii) Cumberland ankle instability tool (CAIT).

Comparison will be tested by using the Paired t test to find the significant difference within the intervention effects and between the two groups (Experimental control group and Experimental Group) using independent t-test. P values <0.05 has been considered statistically significant.

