By combining conventional physiotherapy with relaxation techniques like three typical yoga postures and deep breathing technique, our method not only helps people with Kinesio phobia but also improves their ankle range of motion, balance, and coordination so they can actively resume their daily lives.

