3.3 Recruitment

All amateur football players with Kinesio phobia along Chronic ankle instability attending Saveetha Institute of Medical and Technical sciences will be enrolled in the comparative study. The participation information and consent sheet will be distributed to amateur players which details including inclusion and exclusion criteria. Amateur players who agree to the investigation will be invited to undergo baseline assessments Tampa scale, Pain anxiety symptom scale, Y-balance test, Cumberland ankle instability tool (CAIT). All amateur players will have to return a signed consent form to the site principal investigator.

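### Sections 4.1 and 4.2 name a within-arm paired t-test and an independent t-test for the experimental-versus-control comparison, both at P<0.05, without saying that only the between-group test answers it

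*Combined protocol and SAP*

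**What the plan says.** Section 4.1 of the SAP gives the aim for the Tampa scale and CAIT: "The primary analyses will compare experimental vs control group guidelines on their mean and standard deviation". The next sentence gives the method. Its first half is "Comparison will be tested by using the Paired t test to find the significant difference within the intervention effects". Its second half is "between the two groups (Experimental control group and Experimental Group) using independent t-test. P values <0.05 has been considered statistically significant".

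Section 4.2 has the same structure for the two secondary outcomes. It will "compare experimental vs control group guidelines on their mean and standard deviation: (i) Y-balance test (ii) Pain anxiety symptom scale", followed by the same sentence on paired and independent t-tests and the same threshold.

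Three other places bear on the point:

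- Section 3.3 (Recruitment) has players "invited to undergo baseline assessments Tampa scale, Pain anxiety symptom scale, Y-balance test, Cumberland ankle instability tool (CAIT", so a baseline score is collected for all four outcomes.
- Section 2.1 describes the approach as "By combining conventional physiotherapy with relaxation techniques like three typical yoga postures and deep breathing technique", and section 3.4 gives the breathing component as "6 deep breaths per minute session along with the CP protocol 5 times a week for 3 weeks". Physiotherapy therefore accompanies other components, although the text reviewed does not say which components each arm receives.
- Section 4.3 fills in missed assessments: "the mean imputation of the assessment scores from their allocation group has been used".

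Sections 4 to 4.3 do not rank the two tests, label the paired tests descriptive, or say what to conclude when the tests disagree. They also do not say whether the independent t-test uses follow-up or change scores.

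**The concern.** A paired test in one arm uses no data from the other arm, so it cannot answer a question about experimental against control. The change it measures contains any effect of the experimental element, and also the passage of time, practice on the tests, regression to the mean and any physiotherapy given in that arm. Comparing the two paired P values does not repair this. One arm can fall below 0.05 and the other above it by chance when the true changes are equal.

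The method sentence has a single subject, the comparison, which governs both tests. A reader who follows it literally could report a significant paired test as a positive result for any of the four outcomes.

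There is a second, smaller loss. The independent t-test is stated without the baseline score. If it is run on follow-up scores, it discards information that the trial already holds.

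**Working it through.** **Reading.** On this point the plan has one numerical figure, the 0.05 threshold. It is a convention, so there is nothing to reproduce. Set side by side, the aim is between-group, the first test named is within-arm, the second is between-group, and the threshold covers both. The finding rests on that reading; the figures below only illustrate it.

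**Assumed inputs** (none is in the text reviewed): n = 20 per arm; outcome SD 1 before and after; pre-post correlation r = 0.8; the same true change d = 0.5 SD in both arms, hence no group difference; complete data; two-sided 0.05.

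**Paired test in the experimental arm.**
- SD of change = √(2(1 − r)) = √0.4 = 0.632.
- Noncentrality = (d / 0.632) × √20 = 0.791 × 4.472 = 3.54, with 19 degrees of freedom and critical value 2.093.
- Probability of significance from the noncentral t distribution = 0.918. Simulation of 40,000 trials gives 0.92.

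**Experimental arm significant, control arm not.** With independent arms this is p(1 − p) = 0.918 × 0.082 = 0.075. It cannot exceed 0.25, a value reached when p = 0.5. At d = 0.3 and r = 0.8, p = 0.521 and the result is 0.250.

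**Between-group test.** On follow-up scores, on change scores or by ANCOVA, it is significant in about 5% of simulated trials.

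**Sensitivity.** At 20 per arm the paired figure runs from 19% (d 0.2, r 0.7) to 100% (d 0.8, r 0.9). The between-group figure stays at about 5%.

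**Precision of the between-group estimate** (n = 20, r = 0.8, mean width of the 95% CI). The width is about 2 × t × √(2/n) × SD.
- Follow-up scores: 2 × 2.024 × 0.316 × 1 = 1.28, or 1.27 SD after averaging over the estimated SD.
- Change scores: 1.27 × 0.632 = 0.80 SD.
- ANCOVA: the residual SD is √(1 − 0.8²) = 0.6. The simulated mean width, which includes the cost of estimating the slope, is 0.77 SD.

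**Two conditions on ANCOVA**, both simulated with n = 20 and no true difference in change.
- *Baseline comparability.* If the arms truly differed at baseline by an assumed 0.5 SD, ANCOVA gives about 8% false positives at r 0.8 and 10% at r 0.7. Change scores give 5% and the follow-up t-test 34%.
- *Imputation under section 4.3.* False-positive rates at d 0.5, r 0.8:

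| Follow-up scores filled in | Follow-up t-test | Change t-test | ANCOVA |
|---|---|---|---|
| 10% | 8% | 6% | 8% |
| 20% | 12% | 7% | 12% |
| 30% | 17% | 9% | 18% |

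**The case against.** The strongest reply is that the plan already contains the right test. Section 4.1 opens with the experimental-versus-control aim, and the method sentence gives each test its own question: the paired test for change within, the independent test for the difference between the groups. On that view only the loose word comparison causes the trouble, and reporting paired tests alongside is common.

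Much of this stands. A reader might infer that the plan has adopted a rule under which a paired result counts as success, or that it lacks a between-group test. The documents support neither reading: the independent t-test is planned for all four outcomes, and no section says that a paired result will support a claim against control. A reader might also take the 92% for the plan's false-positive rate. It is the power of a paired test to detect a change that was assumed real, and it becomes an error rate only if that test is used to claim a group difference.

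The objection to ANCOVA stands in part. One sentence making the independent t-test decisive would cure the wording. If that test was to use change scores, the gain in precision is small. ANCOVA also relies on groups comparable at baseline, and the text reviewed mentions allocation groups but does not state randomisation.

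What survives is that the two tests share one stated purpose and one threshold, with no ranking. A prespecified plan should not leave that to the reader.

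**Conclusion.** The concern holds as a gap in the decision rule for all four outcomes. The correct test is present; what is missing is the statement that it alone answers the question. The change should be made, but this is not a case of an absent or invalid primary test.

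Confidence is high on the wording, which depends on no assumed number. The contrast of about 92% with about 5% is an illustration and moves with the assumed sample size, correlation and change.

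The case for baseline adjustment is conditional. At r 0.8 the CI narrows from 1.27 to 0.77 SD if follow-up scores were intended, but only from 0.80 to 0.77 SD if change scores were. It also assumes randomised allocation and the use of observed rather than group-mean-imputed scores. The imputation in section 4.3 is a separate issue, which this change does not settle.

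**What to change.** In sections 4.1 and 4.2:

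1. State that conclusions about experimental against control rest only on the between-group difference with its 95% CI.
2. Estimate that difference by ANCOVA of the follow-up score on the baseline score listed in section 3.3, in place of the unadjusted independent t-test. Use observed scores, not the group-mean-imputed scores of section 4.3.
3. State whether allocation is randomised. If it is not, report the between-group difference in change scores as well.
4. Report within-arm changes with 95% CIs as description only. Label any paired P value that is kept as descriptive and supporting no conclusion.

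The cost is SAP wording and a slightly longer analysis, with no new data. Paired P values can no longer support a conclusion. Until section 4.3 is revised, players without a follow-up score do not contribute to this estimate.

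### Sections 4.1 and 4.2 do not say which score the between-group t-test compares and plan no baseline adjustment for it; under random allocation, ANCOVA would usually be more precise.

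*Combined protocol and SAP*

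**What the plan says.** - **Between-group test.** Section 4.1 opens with "The primary analyses will compare experimental vs control group guidelines on their mean and standard deviation" and then specifies a test "between the two groups (Experimental control group and Experimental Group) using independent t-test". Section 4.2 uses the same sentences for Y-balance and pain anxiety. Neither names the time point or the change, and neither names a covariate. The threshold is "P values <0.05 has been considered statistically significant", with sidedness not given.
- **Within-group test.** Both sections also plan a paired test: "Comparison will be tested by using the Paired t test to find the significant difference within the intervention effects". The time points are not named, but the pairing can only sensibly be baseline with follow-up.
- **Baseline data.** Under 3.3, players who agree "will be invited to undergo baseline assessments Tampa scale, Pain anxiety symptom scale, Y-balance test, Cumberland ankle instability tool (CAIT"), which covers both primary and both secondary outcomes.
- **Y-balance.** Section 3.5.2 gives formulas for absolute, relative and composite reach, for example "Relative (normalised) reach distance (%) = Absolute reach distance / limb length * 100". Section 4.2 does not say which is compared.
- **Design.** Section 3.1 states "The study aims to perform a comparative study on chronic ankle instability with Kinesio phobia". Section 4.3 refers to allocation: "the mean imputation of the assessment scores from their allocation group has been used". Neither says how players are allocated.

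**The concern.** The main between-group result is not uniquely defined. A t-test on the post-intervention score and one on the change score are different tests with different precision, and they can disagree on the same data. While the score is unnamed, it can be picked after the results are seen, and the 5% level then no longer holds.

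A baseline value of every outcome will also be available, but no adjusted between-group comparison is planned. The paired tests use baseline only inside each group and do not compare the groups. If the post score is what gets compared, baseline plays no part in that comparison. Under random allocation the usual consequence is lost precision.

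**Working it through.** **Inputs.** The available text gives no sample size, SD, effect size or correlation, so there is no plan figure to reproduce. From the documents: alpha 0.05, two groups, baseline measured. Assumed: two-sided test, equal random allocation, n per arm of 30 or 15, correlation r between baseline and follow-up of 0.3, 0.5 or 0.7, and equal SDs at both times unless stated.

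**Step 1: variance of the group difference relative to a post-score test.**
- Post score: 1
- Change score: 2(1 − r)
- ANCOVA: 1 − r² in large samples; (1 − r²)(1 + 1/(2n − 4)) in small ones

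**Step 2: power** (noncentral t; 2n − 2 df for the t-tests, 2n − 3 for ANCOVA). The effect is set so that the post-score test has 80% power: 0.7356 SD at 30 per arm, 1.0598 SD at 15. Example at n = 30, r = 0.5: the ANCOVA factor is 0.75 × (1 + 1/56) = 0.763, the standard error is √(0.763 × 2/30) = 0.226, the noncentrality is 0.7356/0.226 = 3.26, and power is 89%.

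| n per arm | r | Post | Change | ANCOVA |
|---|---|---|---|---|
| 30 | 0.3 | 80% | 66% | 83% |
| 30 | 0.5 | 80% | 80% | 89% |
| 30 | 0.7 | 80% | 95% | 97% |
| 15 | 0.3 | 80% | 66% | 82% |
| 15 | 0.5 | 80% | 80% | 89% |
| 15 | 0.7 | 80% | 95% | 97% |

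**Step 3: where ANCOVA does not win.** Setting (1 − r²)(1 + 1/(2n − 4)) = 1 gives r = 1/√(2n − 3): 1/√57 = 0.13 at 30 per arm and 1/√27 = 0.19 at 15. Below these values ANCOVA is slightly worse than the post score. At r = 0 its power is 79.3% (30 per arm) or 78.4% (15 per arm) against 80%. With equal SDs the change score overtakes it only above r = 0.965 (30 per arm) or 0.926 (15 per arm). With unequal SDs that can happen sooner. If the follow-up SD is 1.25 times the baseline SD, n = 15 and r = 0.7, the change factor is 1 + 1/1.25² − 2(0.7)/1.25 = 0.520 against 0.530 for ANCOVA.

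**Step 4: cost of leaving the score open.** In simulated null trials with 30 per arm, always reporting the smaller of the post and change p-values gives type I error of 8.8, 9.1 and 9.3% at r = 0.3, 0.5 and 0.7. This is a worst case.

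**Step 5: if allocation is not random.** Assume a true baseline gap D = 0.3 SD and no treatment effect. At r = 0.3 / 0.5 / 0.7 the expected bias in SD units is:
- One regression on baseline shared by both groups: post rD = 0.09 / 0.15 / 0.21; change (r − 1)D = −0.21 / −0.15 / −0.09; ANCOVA 0.
- Parallel untreated trends: post D = 0.30; change 0; ANCOVA (1 − r)D = 0.21 / 0.15 / 0.09.

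The methods then have different expected values, so the variance ratios of Step 1 do not rank them.

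**Step 6: interaction with 4.3.** With 30 per arm and 3 or 6 scores per arm replaced by the group mean, simulated type I error is about 0.077 or 0.117, for the t-test and ANCOVA alike.

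**The case against.** The strongest reply is that the t-test is not an error. Under random allocation a t-test on either score is valid, naming one score in a single phrase would close the specification gap, and ANCOVA is then a preference. That stands as far as validity goes, but only with complete data and a score named in advance. The precision argument for ANCOVA remains, because the baseline data are already being collected.

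A reader might infer more than the documents support:
- *That the baseline goes unused.* It does not: the paired tests use it within groups, and a change-score t-test would use it between groups too. What is missing is a specified baseline adjustment of the between-group comparison.
- *That ANCOVA is better whatever the design.* Its precision advantage depends on random allocation, which the available text neither states nor rules out. Under non-random allocation it may reduce baseline bias but need not remove it.
- *That the type I error will be about 9%.* That figure supposes the smaller p-value is always reported, and nothing in the plan suggests this is intended.

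It is also fair to say that every magnitude rests on assumed arm sizes and correlations, and that the imputation rule in 4.3 is a separate defect. It matters here only because any between-group model fitted to group-mean-filled scores would not keep its level.

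**Conclusion.** The point holds in limited form. The outcome variable of the between-group test is undefined in 4.1 and 4.2, and no baseline adjustment is specified for it. With random allocation, complete data and a pre-named score, the loss is precision only. At an assumed 30 per arm with equal SDs, ANCOVA gains about 3 to 17 percentage points of power over the post score for r from 0.3 to 0.7 (83 − 80 to 97 − 80), and about 2 to 17 points over the change score (97 − 95 to 83 − 66). It loses under 1 point against the post score at r = 0. If allocation is not random, precision is not the main question, and neither ANCOVA nor the change score can be said to remove baseline bias. This should be changed, because it is cheap and settles the primary comparison, but it is not a fatal flaw.

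Y-balance has a related gap. If the three reaches in 3.5.2 are the three directions, the relative and composite formulas coincide; if they are repeat trials, there is a separate absolute and relative value for each direction. Under either reading more than one measure is available and 4.2 names none.

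**What to change.** In 4.1 and 4.2, replace the between-group sentence with wording such as: *The between-group analysis of each outcome is an ANCOVA with the post-intervention score as outcome, group as factor and the baseline value of the same score as covariate. The adjusted difference with its 95% confidence interval is the result. For Y-balance, one named reach measure is used at both times.*

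Add: *The model is fitted to observed post-intervention scores, with players in their allocated group, and the number missing is reported per group.* This is valid if scores are missing at random given group and baseline. The group-mean imputation in 4.3 should not feed this model, and that rule needs its own correction.

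State the allocation method. If it is not random, say so and report the ANCOVA and change-score differences side by side, noting that they rest on different assumptions and claiming for neither that it removes baseline bias.

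If the sponsor prefers to keep the t-test, the minimum is to name the score in both sections before any outcome data are seen.

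Cost: SAP wording only. The baseline scores are already planned and the named software fits the model, so no extra participants or visits are needed. The statistical price is one degree of freedom, an assumed linear slope common to both groups, and a slight loss if r is near zero or, in small arms, if the regression slope is near 1.
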